4.1.1 Number of Patients Required for Clinical Study and Rationale

No restrictions.

The eligible patients will be included between May 2023 and May 2027, without limiting the sample size of patients. This approach aligns with the NMPA requirements, which state, “Each product implanted in a patient shall be registered, and all patients implanted with the product shall be followed

up for a long time". By not imposing a limit on the number of enrolled patients, the study ensures that all eligible patients can participate, enabling a comprehensive assessment of the safety and efficacy of the FRED.

Moreover, this flexible recruitment strategy enhances sample diversity, allowing for a more accurate reflection of real-world clinical applications. A larger and more varied sample will facilitate a thorough analysis of outcomes across different patient demographics and conditions, ultimately strengthening the reliability of the study's findings and their applicability in clinical practice.

4.1.2 Expected Overall Duration of Clinical Study

About 36months.

4.2 Patient Selection

4.2.1 Inclusion Criteria

A patient is eligible for inclusion in the study if he/she meets all the following criteria:

- 1) People in China mainland who have been treated with FRED.
- 2) The patients for whom clinical data are available.

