4.1 Overall Design and Selection Rationale

This is a post-market, retrospective, multi-center, observational clinical study.

The study plans to enroll patients who meet the eligibility criteria and have received at least one implantation of the observational device between May 2023 and May 2027. The retrospective data will be collected on baseline characteristics, information of procedure, and safety and efficacy endpoint to assess the safety and efficacy of FRED in the Chinese population. The efficacy endpoints include technical success rates and re-sheathing performance, the complete occlusion rate, and modified Rankin Scale (mRS) change from baseline. The safety endpoints include the rates of stroke, mortality, lesion-related symptoms or signs rate, lesion-related complication rate, adverse event, serious adverse event.

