4.2.2 Exclusion Criteria

Patients who met the inclusion criteria at all time points were required to be included in the study. Therefore, no specific exclusion criteria were set.

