4.5 The Data Collection Schedule

The data collection schedule is described in

Table 4-3 Data Collection Plan

Baseline	Treatment*	Follow-Up Information**

Demographic Information¹Medical History²Physical Examination³Imaging findings⁴Modified Rankin ScaleAneurysm Information⁵Laboratory Examination⁶Information of antiplatelet function test result: platelet aggregation test/ Thromboelastographic (TEG)Information of anti-coagulation and anti-platelet medication⁷	
Using Information of DeviceInformation of ProcedureStrokeMortalityAE/SAEO'Kelly-Marotta(OKM) GradeRaymond-Roy GradeTechnical SuccessRe-sheathing Performance	
Physical Examination⁴Information of anti-coagulation and anti-platelet medication⁷Image dataLesion-Related ComplicationStrokeMortalityAE/SAE⁸O'Kelly-Marotta(OKM) GradeRaymond-Roy gradeModified Rankin Scale

Notes:

1. Demographic Information including: birth date, sex, history of smoking and drinking, ethnicity, diagnosis.
2. Medical History: Past medical history: including current medical conditions (high blood pressure, diabetes, etc.), history of cranial and neurological related surgeries, hemorrhagic stroke.

3. Physical Examination: neurological physical examination.

4. Image data collection, per standard of care (e.g., DSA, MRA, CTA) can be applied.

5. Based on CTA .

6. Laboratory Examination: Blood routine (red blood cell count, hemoglobin white blood cell count, neutrophil count, lymphocytes count, platelet count), coagulation test [Prothrombin Time (PT), Activated Partial Thromboplastin Time (APTT), Thrombin Time (TT) and Fibrinogen (FIB) International standardized ratio (INR)]. Only clinically significant abnormal results were recorded.

7. Information on anti-coagulation and anti-platelet medication: drug name, dosage and frequency of administration are needed.

*. If the same patient received other surgical treatments using observational device within the data collection time frame, only the first treatment data was selected as the baseline data, and the follow-up time was calculated at this point. The remaining surgical treatments were recorded as "concomitant surgery".

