5.2 Statistical Analysis Datasets

The dataset will consist of all study patients who meet the inclusion and exclusion criteria.

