6.1 Data Capture

Electronic Data Capture (EDC) will be used in this study, and clinical study data will be entered into eCRF by the investigators or authorized staff at the clinical research institutions. The investigators and authorized staff at the clinical research institutions will receive appropriate trainings before the initiation of clinical research institutions or data entering and appropriate measures will be adopted to protect the security of data.

The investigators will be responsible for maintaining all source documents and ensure they can be monitored by CRAs at each visit. In addition, the investigators shall submit a complete eCRF for every patient participating in the study, regardless of the duration of participation. The study number and patient number in all supporting documents (e.g., clinical research institution records) submitted with eCRF shall be checked carefully and all individual privacy (including the name of patient) shall be deleted, or measures shall be taken to make it difficult to identify patients to protect the privacy of patients.

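### Eligibility is not tied to the hospital that implanted the FRED, so patients who reach a participating site because of a complication can enter the endpoint rates, and no rule assigns a patient to one site

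*Protocol*

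**What the plan says.** Section 4.2.1 of the Protocol, repeated in the synopsis, sets two inclusion criteria: "People in China mainland who have been treated with FRED" and "The patients for whom clinical data are available". Section 4.2.2 sets no exclusions and gives the reason: "Patients who met the inclusion criteria at all time points were required to be included in the study". Section 4.1 describes the design ("This is a post-market, retrospective, multi-center, observational clinical study") and limits enrolment to eligible patients who "have received at least one implantation of the observational device between May 2023 and May 2027". That restricts the date of implantation, not the place.

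Section 5.2 defines the analysis set: "The dataset will consist of all study patients who meet the inclusion and exclusion criteria". Section 4.4.1 takes the stroke, mortality, symptom and complication rates over all patients, and section 4.4.2 does the same for occlusion and technical success.

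The only rule about one patient appearing more than once is the asterisked note to Table 4-3 in section 4.5. For repeat FRED procedures within the collection period, "only the first treatment data was selected as the baseline data, and the follow-up time was calculated at this point".

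**The concern.** In a retrospective multi-centre study the population should be defined by the exposure, here implantation at a participating centre, and not by how a patient came to be in a centre's files. Criterion 1 does not do this. Two consequences follow.

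- **Entry that depends on outcome.** Someone implanted at a non-participating hospital may be transferred to a participating site because of a stroke, a haemorrhage or an aneurysm that still fills. That person has been treated with FRED in mainland China and has clinical data at the site. Patients from the same implanting hospital who do well have little reason to appear there. The referred group brings events without its event-free counterpart.
- **No owner for the record.** If both hospitals take part, the patient can satisfy the criteria at both. The protocol does not say which site enters the patient or how the two charts are joined.

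Section 4.6 relies on enrolling all eligible patients in the time frame to avoid selection bias. With eligibility open in this way, that safeguard does not keep the selected patients out. The exact binomial interval of section 5.3.4 reflects sampling error only and would not show the bias.

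**Working it through.** **Step 1. Is the implanting site fixed anywhere?**

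| Place | What it restricts | Implanting site? |
|---|---|---|
| 4.1 | Date of implantation, May 2023 to May 2027 | No |
| 4.2.1, criterion 1 | Country and device | No |
| 4.2.1, criterion 2 | Clinical data available, not defined further | No |
| 4.2.2 | No exclusions; inclusion compulsory | No |
| 4.5, note * | Which procedure is baseline for a given patient | No |
| 5.2 | All who meet the criteria | No |

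No provision ties the patient to the implanting institution, and none says which of two participating sites enters a shared patient.

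**Step 2. Direction.** Let N patients be implanted at participating sites, with x events and rate p = x/N. Add a referred patients with event proportion q.

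Observed rate = (x + aq)/(N + a)

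Shift = a(q − p)/(N + a)

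The shift is zero if q = p and positive if q > p. Patients who arrive because of a complication have q > p by the way they are selected. For occlusion the sign reverses when the reason for arrival is persistent filling.

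**Step 3. Illustrative size.** The protocol states no sample size, event rate or referral share, so there is no figure of its own to reproduce. Every input here is an assumption. Intervals are exact (Clopper-Pearson), the method named in section 5.3.4.

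| Assumed scenario | Strokes / patients | Rate | Exact 95% CI |
|---|---|---|---|
| Implanted at participating sites only | 15/300 | 5.0% | 2.8 to 8.1% |
| Plus 6 referred, 3 strokes | 18/306 | 5.9% | 3.5 to 9.1% |
| Plus 15 referred, 8 strokes | 23/315 | 7.3% | 4.7 to 10.8% |

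Check against the shift formula:
- 6 referred: (3 − 6 × 0.05)/306 = 2.7/306 = 0.9 percentage points.
- 15 referred: (8 − 15 × 0.05)/315 = 7.25/315 = 2.3 percentage points.

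Both scenarios assume that about half of the referred patients had a stroke (3/6 and 8/15). The shift shrinks in proportion as q approaches p.

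**Step 4. Double entry, same starting point.** If 4 of the 15 stroke patients were each entered at two sites, the rate would be (15 + 4)/(300 + 4) = 19/304 = 6.3%. The 4 is also an assumption. The calculation shows only that duplicating patients with events moves the rate the same way.

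**The case against.** The best defence is that the implanting hospital's chart was plainly meant. Section 4.3.3 collects FRED model and lot number, microcatheter, re-sheathing attempts and immediate imaging, which a receiving hospital would rarely hold. Section 7.1 expects complete diagnosis and treatment records at each institution. On that reading a referred patient fails criterion 2. This has weight, and it is why one should not say that sites *must* enrol such patients: that depends on what available clinical data means. But the term is undefined, no rule states the intended reading, and section 8.2 has unavailable items recorded in the eCRF without making them a ground for exclusion. Two sites could reasonably decide differently.

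The referral bias also needs implanting hospitals outside the study. The protocol does not give the number or coverage of sites. If every implanting hospital took part, only the question of which site enters the patient would remain. This stands as a limit.

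On duplication, a reader might infer three stronger things that the document does not support.

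- *Patients will be counted twice.* The text leaves this open but does not prescribe it. Sections 4.6 and 6.3 provide a review of the analysis population before lock, and detailed duplicate checks can sit in a data management plan.
- *A retreating site may restart the follow-up clock.* The note in section 4.5 already makes the first procedure in the window the baseline for the same patient, and section 4.3.2 collects earlier cranial surgery. Restarting the clock would breach the rule.
- *De-identification prevents matching.* The words "all individual privacy (including the name of patient) shall be deleted" in section 6.1 concern supporting documents submitted with the eCRF, and the sentence goes on to allow masking instead. Birth date, sex, model and lot number remain eCRF items, and section 15 lists the identity card among data held by investigators.

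Finally, section 4.1.1 justifies the study by a regulatory demand to follow all implanted patients. Dropping referred patients outright would discard known events. That objection is sound and shapes the fix.

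**Conclusion.** The point holds as a gap in a rule that the protocol itself fixes. Criterion 1, with compulsory inclusion and an all-eligible analysis set, leaves the implanting site open and so allows entry that depends on outcome. The direction is clear: stroke, mortality, symptom and SAE rates up, occlusion down. The size is unknown. On the assumed inputs a 5.0% stroke rate would be reported as 5.9% or 7.3%. Even 7.3% lies inside the starting interval of 2.8 to 8.1%, so the effect is a bias worth removing but not one shown to dominate. A reader might conclude that a 5% share of referred patients (15 on 300) raises the stroke rate by almost half (7.3/5.0 = 1.46). That follows only from the assumed 8 strokes in 15 and is not a property of this study. The conclusion rests on two conditions: some implanting hospitals do not take part, and some sites read criterion 2 as met by the records of the complication. The missing assignment of a patient to one site needs only that both hospitals take part.

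**What to change.** Four changes:

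1. In the synopsis and section 4.2.1, state that the patient's first FRED procedure in the collection window was performed at the enrolling participating institution, and that this institution alone enters the patient.
2. State that later data from other participating sites attach to that record.
3. List patients implanted at non-participating hospitals, with their events, separately and outside the endpoint rates. This keeps known events visible, in line with section 4.1.1, without mixing them into a denominator to which they do not belong.
4. Check for duplicate patients before each stage analysis in section 5.4, using birth date, sex, procedure date, FRED model and, where available, lot number. Sections 4.3.1 and 4.3.3 already collect birth date, sex, model and lot number. Section 4.4.2 needs the surgery date for time to occlusion.

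The cost is a short amendment and a simple matching step, with no new data items. The downside is that a few referred patients leave the main rates. Matching will also be weaker where the second site lacks the lot number, so birth date, sex and procedure date have to carry most of it.

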16.1 Responsibilities of Sponsor.....	32

16.2 Responsibilities of Medical Device Clinical Research Institutions	33
16.3 Responsibilities of Investigators	34
17 Miscellaneous Issues to be Clarified.....	34
17.1 Finance and Insurance.....	34
17.2 Agreement on Study Result Publication	34
Investigator Statement.....	35
References	36
List of Figures	
Figure 2-1 FRED System Setup.....	15
Figure 2-2 FRED Implant Nomenclature.....	15

List of Tables

Table2-1 List of Specifications and Models	15
Table 4-1 Raymond-Roy Classification Standards	21
Table 4-2 Modified Rankin Scale (mRS).....	22

List of Abbreviations

Abbreviation	Full Term
AE	Adverse Event
APTT	Activated Partial Thromboplastin Time
CEC	Clinical Event Committee
CI	Confidence Interval
CRA	Clinical Research Associates
CRO	Contract Research Organization
CTA	Computed Tomography Angiography
CS	Clinically Significant
CSR	Clinical Study Report
DSA	Digital Subtraction Angiography
EC	Ethics Committee
eCRF	electronic Case Report Form
EDC	Electronic Data Capture
FD	Flow Diverter
FIB	Fibrinogen
FRED	Flow Re-Direction Endoluminal Device
GCP	Good Clinical Practice
IA	Intracranial Aneurysms
ICF	Informed Consent Form
IFU	Instructions For Use
MRA	Magnetic Resonance Angiography
mRS	modified Rankin Scale
NMPA	National Medical Products Administration
OKM	O'Kelly-Marotta
PD	Protocol Deviation
PED	Pipeline Embolization Device
PI	Principal Investigator
PT	Prothrombin Time
SAE	Serious Adverse Event
SAH	Subarachnoid Hemorrhage
SAP	Statistical Analysis Plan
SAR	Statistical Analysis Report
SDV	Source Data Verification
TEG	thromboelastographic
TT	Thrombin Time
UIA	Unruptured Intracranial Aneurysms

Protocol Synopsis

Sponsor	MicroVention, Inc.
Study Title	A retrospective, post-market clinical study of the flow re-direction endoluminal device system in the treatment of intracranial aneurysms.
Protocol No.	CL1106094
Version/Date	Version A, 2025-01-21
Study Objective	To evaluate the long-term safety and efficacy of Flow Re-Direction Endoluminal Device System (FRED) in the treatment of intracranial aneurysms in the post-market environment
Study Design	Post-market, retrospective, multi-center, observational clinical study
Study Population	Patient who has implanted at least one observational device in China mainland.
Observational Device	Flow Re-Direction Endoluminal Device System (FRED)
Study Duration	About 36 months.

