4.6 Bias Control Measures

Multicenter Study: A multicenter design ensures that the case sample is more representative compared to a single-center study, thereby reducing the potential for bias caused by systemic errors

unique to a single center. This enhances the generalizability of the study results.

Standardized Data Collection: The eligible patients meeting the inclusion within the specified time frame, will be enrolled in this study to avoid selection bias. This ensures the integrity of the population under study and minimizes the risk of bias introduced by arbitrary patient selection.

Training of Data Recorders: Data collection personnel will undergo comprehensive training to ensure that all data are captured uniformly, in accordance with predefined data collection protocols and eCRF standards. Regular data audits and quality control procedures will be implemented to ensure the accuracy, reliability, and completeness of the data.

Data Review: Prior to database lock, a data review meeting will be initiated by the data management team. Attendees will include the principal investigator, the sponsor, data managers, clinical monitors, and biostatisticians. The primary objectives will be to finalize the statistical analysis dataset, evaluate any unreported AEs, verify any outstanding data queries, and decide on database lock and the formal approval of population stratification decisions.

Investigator Training: All investigators involved in this clinical study are highly experienced in the relevant therapeutic area. Prior to study initiation, Clinical Research Associates (CRAs) will conduct thorough protocol training sessions to ensure investigators are fully knowledgeable about the study design, endpoint definitions, and operational procedures. Investigators will rigorously adhere to the inclusion criteria and will document clinical data according to protocol-defined procedures.

Clinical Study Monitoring: Regular on-site monitoring visits will be conducted to ensure strict adherence to the study protocol. Source Data Verification (SDV) will be performed on eCRF to verify that the data recorded are consistent with the original source documents.

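### Inclusion criterion 2 makes eligibility, and so the safety denominators, depend on undefined data availability, and implanted patients left out are not counted

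*Protocol*

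**What the plan says.** Section 4.2.1 has two inclusion criteria, repeated in the Synopsis: "People in China mainland who have been treated with FRED" and "The patients for whom clinical data are available". Neither the kind of data nor the meaning of available is defined. Section 4.2.2 sets no exclusion criteria.

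The criteria fix the analysis set. Under section 5.2, "The dataset will consist of all study patients who meet the inclusion and exclusion criteria". Section 4.4.1 then defines stroke, all-cause mortality, lesion-related symptoms and lesion-related complications as proportions of the total number of patients.

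Three other places describe the population differently:

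- The Study Population row of the Synopsis carries no data condition: "Patient who has implanted at least one observational device in China mainland".
- Section 4.1.1 says that the open enrolment aligns with a regulatory requirement: "Each product implanted in a patient shall be registered, and all patients implanted with the product shall be followed" up long term. The protocol's own undertaking there is narrower: "the study ensures that all eligible patients can participate".
- Section 4.6 says that eligible patients within the time frame "will be enrolled in this study to avoid selection bias".

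**The concern.** Criterion 2 works as an exclusion although section 4.2.2 says there is none. Because it is undefined, sites can apply it differently. One may admit a patient who has only an operative note; another may ask for at least one follow-up record. The reference in section 4.2.2 to meeting the criteria at all time points leaves room for the second reading. Under that reading, a patient who died elsewhere, moved or never returned would leave the denominator instead of appearing as missing, so selection would depend on what happened after the implant.

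The protocol asks for no list of implants at each site and no count of implanted patients not included. Sections 4.6 and 6.3 also leave the final analysis population to a data review before database lock, when recorded outcomes may already be known. A statistical analysis plan cannot repair this, because patients who were never entered cannot be recovered at analysis.

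At stake is whether the long-term stroke and mortality rates describe all implanted patients or an unknown part of them.

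**Working it through.** The protocol states no sample size, event rate or share of patients without data, so there is no figure to reproduce. The inputs below are assumptions that show how the criterion acts.

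**Step 1. Eligible-only rate against all-implant rate.** Let p be the risk in patients with data (assumed 5%), m the share of implanted patients without data, and RR their risk relative to patients with data. The report shows p. The all-implant rate is p × [(1 − m) + m × RR].

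| m | RR 0.5 | RR 1 | RR 2 | RR 3 |
|---|---|---|---|---|
| 5% | 4.9% | 5.0% | 5.25% | 5.5% |
| 10% | 4.75% | 5.0% | 5.5% | 6.0% |
| 20% | 4.5% | 5.0% | 6.0% | 7.0% |

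For m = 20% and RR = 3: 5% × (0.8 + 0.6) = 7.0%. For m = 20% and RR = 0.5: 5% × (0.8 + 0.1) = 4.5%. The report would show 5.0% in every cell. Its relative error runs from 5.0/4.5 − 1 = +11% to 5.0/7.0 − 1 = −29%, and is zero at RR = 1.

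**Step 2. Returning these patients to the denominator is not enough.** Section 4.4.1 uses simple proportions, and section 5.5 leaves missing safety values unfilled. A patient retained without follow-up would then count as event-free, giving p × (1 − m): 4.75%, 4.5% and 4.0% for m = 5%, 10% and 20%. This falls short of the all-implant rate by p × m × RR, so it is too low whenever those patients have any risk. At m = 20% and RR = 1 the shortfall is 1.0 point.

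**Step 3. What the confidence interval leaves out.** Assume 500 implanted patients, 10% without data, and 22 events in the other 450. The reported rate is 22/450 = 4.9%, with an exact 95% interval of 3.1% to 7.3%. Over all 500, the best case is 22/500 = 4.4% and the worst case is (22 + 50)/500 = 14.4%. The exact binomial interval in section 5.3.4 covers sampling error in the 450 only.

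**The case against.** A reader might infer that the criterion removes every patient with a thin record. The text does not say so. Section 4.2.1 sets no minimum data and does not mention follow-up, so a patient with only a procedure record has clinical data and can qualify. Section 6.1 asks for a complete eCRF for each participant however long the participation, section 8.2 has unavailable items recorded as such, and section 5.5 has rules for missing values. Loss of thin records is therefore one possible reading, not the stated rule. But these sections govern patients already in the study; they do not cover implanted patients whom a site judges not to qualify.

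A reader might also infer a flat contradiction with section 4.1.1. The all-implants sentence there is a quoted regulatory requirement, used to justify having no cap on enrolment, and the protocol's own promise concerns eligible patients. Section 4.6 likewise speaks of eligible patients, and taking all of them does prevent picking among them. Tension is the right word. It remains because the protocol claims alignment with the requirement while eligibility itself selects on data.

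A third inference would be that the safety rates are understated. The documents do not show this. Section 7.1 says that site records are reviewed beforehand and are complete, so a 10% or 20% loss has no support in the text, and the error can go either way.

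Finally, a retrospective study cannot analyse a patient with no record at all. That stands, but such a patient can still be counted.

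**Conclusion.** The concern holds as an undefined eligibility condition that fixes the denominators of the safety rates, with no count of those left out. Bias is a risk, not a demonstrated result; it arises only if patients without data differ in risk, and its direction is open. Under the assumed 5% observed rate, with 20% excluded, the reported figure would overstate the all-implant rate by 0.5 point at a risk ratio of 0.5, match it at 1, and understate it by 2.0 points at 3. All these inputs are assumed. What the protocol does establish is that a reader of the report could not tell what share of implanted patients the rates describe. This should be corrected while data collection can still be adjusted.

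**What to change.** - In section 4.2.1 and the Synopsis, replace criterion 2 with: the record of the index FRED procedure is available; no follow-up data are required.
- List all implants at each site from device and lot records. Section 4.3.3 already collects the lot number for included patients.
- Report per site the numbers implanted, included, not included (with reason) and without follow-up. Patients with no procedure record cannot be analysed but are counted here.
- Keep patients without later records in the denominators of the procedural endpoints.
- Amend section 4.4.1 so that stroke and mortality over follow-up are estimated with censoring at last contact instead of as a simple proportion of all patients. Section 5.3.4 already provides Kaplan-Meier.
- Add best-case and worst-case bounds for patients not included or without follow-up, since censoring assumes that loss is unrelated to risk.

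The cost is an implant tally at each site, and missing-data rates that become visible and may look less favourable.
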